6.3 Efficacy

Samples and measurements will be collected as discussed in this section and according to the schedules presented in Study Plan (Table 1) and Section 6.2.

6.3.1 HbA1c

Blood samples for the measurement of HbA1c will be collected at every visit as specified in the schedules presented in Study Plan (Table 1) and Section 6.2. The centralized laboratory will provide specific instructions for collection, processing, packaging, and shipping of all HbA1c samples.

6.4 Safety

The Principal Investigator is responsible for ensuring that all staff involved in the study is familiar with the content of this section. Safety will be assessed throughout the study by examination of AEs, concomitant medications, clinical laboratory evaluations, antibody measurements, vital signs, physical examinations, and other safety observations. Safety assessments by visit are listed in Sections [6.4.5](#) - [6.4.9](#).

6.4.1 Definition of adverse events

An AE is the development of an undesirable medical condition or the deterioration of a pre-existing medical condition following or during exposure to a pharmaceutical product, whether or not considered causally related to the product. An undesirable medical condition can be symptoms (eg, nausea, chest pain), signs (eg, tachycardia, enlarged liver) or the abnormal results of an investigation (eg, laboratory findings, electrocardiogram). In clinical studies, an AE can include an undesirable medical condition occurring at any time, including run-in or washout periods, even if no study treatment has been administered.

The term AE is used to include both serious and non-serious AEs.

6.4.2 Definitions of serious adverse event

A serious adverse event (SAE) is an AE occurring during any study phase (ie, run-in, treatment, washout, follow-up), that fulfils 1 or more of the following criteria:

- Results in death
- Is immediately life-threatening
- Requires in-patient hospitalization or prolongation of existing hospitalization
- Results in persistent or significant disability/incapacity or substantial disruption of the ability to conduct normal life functions
- Is a congenital abnormality or birth defect
- Is an important medical event that may jeopardise the patient or may require medical intervention to prevent 1 of the outcomes listed above.

For further guidance on the definition of a SAE, see [Appendix B](#) to the Clinical Study Protocol.

6.4.3 Recording of adverse events

All AEs that occur after the patient has signed the informed consent will be recorded on source documents. Adverse events for patients who enroll in the study will be entered on source documents and the eCRFs. Adverse events include those reported spontaneously by the patient and those noted incidentally or as the result of nondirected questioning by the

Investigator or study personnel. To avoid vague, ambiguous, or colloquial expressions, the AE should be recorded on the eCRFs using standard medical terminology that is as specific as possible, rather than the patient's own words. Whenever the Investigator is confident in making a unifying diagnosis, all related signs, symptoms, and abnormal test results should be grouped together as a single AE on the eCRF (eg, cough and rhinitis should be reported as an "upper respiratory tract infection"). Adverse events will be evaluated for intensity and causal relationship with the use of the study medication by the Investigator.

Time period for collection of adverse events

Adverse Events will be collected from time of signature of informed consent, throughout the treatment period and including the follow-up period.

All clinically significant abnormalities noted upon physical examination, ECG, and clinical laboratory and vital sign measurements that occur during the study and were not present prior to the signing of the ICF, should be reported as an AE, except for abnormalities present at Screening that may be considered part of the medical history.

Follow-up of unresolved adverse events

All clinically significant AEs that are unresolved at Study Termination are followed up by the Investigator and evaluated with additional tests if necessary, until the underlying cause is diagnosed or resolution occurs. AstraZeneca retains the right to request additional information for any patient with ongoing AEs/SAEs at the end of the study, if judged necessary. Follow-up information should be recorded on the source documents and reported to the Sponsor.

Adverse events that occur following completion of study termination/early termination procedures should be recorded on the AE page of the eCRF only if the Investigator considers the event as clinically significant and as related to study medication or study procedures. All SAEs that occur within 90 days of administration of the last dose of study medication (regardless of causality) must be reported immediately (Section 6.4.4). Concomitant medications used following study termination procedures should be recorded only if relevant to treatment of patients for events described above.

Variables

The following variables will be collect for each AE:

- AE (verbatim)
- The date when the AE started and stopped
- If AE is of maximum intensity
- Whether the AE is serious or not
- Investigator causality rating against the Investigational Product (yes or no)

- Action taken with regard to investigational product
- AE caused patient's withdrawal from study (yes or no)
- Outcome.

In addition, the following variables will be collected for SAEs:

- Date AE met criteria for serious AE
- Date Investigator became aware of serious AE
- AE is serious due to
- Date of hospitalization
- Date of discharge
- Probable cause of death
- Date of death
- Autopsy performed
- Causality assessment in relation to Study procedure(s)
- Causality assessment in relation to Other medication
- Description of AE.

6.4.3.1 Intensity

It is important to distinguish between serious and severe AEs. Severity is a measure of intensity whereas seriousness is defined by the criteria in Section 6.4.2. An AE of severe intensity need not necessarily be considered serious. For eg, nausea that persists for several hours may be considered severe nausea, but not an SAE. On the other hand, a stroke that results in only a limited degree of disability may be considered a mild stroke but would be an SAE.

The intensity of each AE will be characterized as MILD, MODERATE, or SEVERE, as follows:

MILD: Usually transient, requires no special treatment, and does not interfere with the patient's daily activities.

MODERATE: Usually causes a low level of inconvenience or concern to the patient and may interfere with daily activities, but is usually ameliorated by simple therapeutic measures.

SEVERE: Interrupts a patient's usual daily activities and generally requires systemic drug therapy or other treatment.

6.4.3.2 Causality collection

The Investigator will assess causal relationship between Investigational Product and each AE, and answer 'yes' or 'no' to the question 'Do you consider that there is a reasonable possibility that the event may have been caused by the investigational product?'

For SAEs, causal relationship will also be assessed for other medication and study procedures. Note that for SAEs that could be associated with any study procedure, the causal relationship is implied as 'yes'.

The Investigator will grade the association of the AE as NOT RELATED or RELATED to study medication. The following criteria should be considered for determining relatedness:

NOT RELATED: The AE is judged to be produced by the patient's clinical state or by other therapies administered to the patient.

RELATED: The AE is judged to be related to the administration of study medication.

A guide to the interpretation of the causality question is found in [Appendix B](#) to the Clinical Study Protocol.

6.4.3.3 Hypoglycemia

All patients will be asked to record a blood glucose measurement if they experience symptoms of hypoglycemia. Patients will be instructed to report any symptoms of hypoglycemia and blood glucose values associated with these symptoms.

If the clinician determines that a patient experienced symptoms consistent with hypoglycemia, the event should be documented in the patient's source documentation and the hypoglycemia AE eCRF page must be completed. If a blood glucose value of <54 mg/dL (3.0 mmol/L) is noted within the data, which is asymptomatic, the clinician should assess whether the circumstances around the value are consistent with hypoglycemia. If the assessment is that the value is consistent with hypoglycemia, the hypoglycemia AE eCRF page should be completed. Study-site personnel must obtain accurate information for the patient's file and for the hypoglycemia AE page of the eCRF. If the hypoglycemic episode intensity is classified as severe, the Investigator is required to contact the Sponsor.

The criteria for evaluating the intensity of a hypoglycemic episode are the following:

MILD: Usually transient, requires no special treatment, and does not interfere with the patient's daily activities.

MODERATE: Usually causes a low level of inconvenience or concern to the patient and may interfere with daily activities, but is usually ameliorated by simple therapeutic measures.

SEVERE: Requires the assistance of another person to obtain treatment (eg, intravenous glucose, intramuscular glucagon, or oral carbohydrate) for the event.

Adverse Events based on signs and symptoms

All AEs spontaneously reported by the patient or care provider or reported in response to the open question from the study personnel: Have you had any health problems since the previous visit/you were last asked?, or revealed by observation will be collected and recorded in the eCRF. When collecting AEs, the recording of diagnoses is preferred (when possible) to recording a list of signs and symptoms. However, if a diagnosis is known and there are other signs or symptoms that are not generally part of the diagnosis, the diagnosis and each sign or symptom will be recorded separately.

Adverse Events based on examinations and tests

The results from protocol mandated laboratory tests and vital signs will be summarized in the clinical study report. Deterioration as compared to baseline in protocol-mandated laboratory values and vital signs should therefore only be reported as AEs if they fulfil any of the SAE criteria or are the reason for discontinuation of treatment with the investigational product.

If deterioration in a laboratory value/vital sign is associated with clinical signs and symptoms, the sign or symptom will be reported as an AE and the associated laboratory result/vital sign will be considered as additional information. Wherever possible the reporting Investigator uses the clinical, rather than the laboratory term (eg, anaemia versus low hemoglobin value). In the absence of clinical signs or symptoms, clinically relevant deteriorations in non-mandated parameters should be reported as AEs.

Deterioration of a laboratory value, which is unequivocally due to disease progression, should not be reported as an AE.

Any new or aggravated clinically relevant abnormal medical finding at a physical examination as compared with the baseline assessment will be reported as an AE.

NB. Cases where a patient shows an aspartate aminotransferase (AST) **or** alanine aminotransferase (ALT) $\geq 3 \times$ ULN **and** total bilirubin $\geq 2 \times$ ULN must be reported as SAEs, please refer to [Appendix D](#) 'Actions Required in Cases of Increases in Liver Biochemistry and Evaluation of Hy's Law', for further instructions.

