3.4 Safety variables

- Corresponding to the primary safety objective, safety and tolerability endpoints including the incidence of treatment emergent AEs (TEAEs; see section 4.2.4.1), antibodies to exenatide, physical examinations, laboratory measurements (clinical, chemistry/hematology), and vital sign measurements from baseline Visit 2 (Week 0) to Visit 7 (Week 24), Visit 10 (Week 52), and to each intermediate visit as applicable
- Proportions of patients reporting different injection site reactions at Visit 3 (Week 4) through Visit 10 (Week 52) (see Section 4.2.4.2 for details of injection site reaction reporting)
- Change in calcitonin, pancreatic amylase, and lipase from baseline Visit 2 (Week 0) to Visit 5 (Week 12) and Visit 10 (Week 52)

- Change in Thyroid-stimulating hormone (TSH), thyroxine (free T4), prolactin, cortisol, insulin-like growth factor 1 (IGF-1), and Dehydroepiandrosterone (DHEAS) from baseline Visit 2 (Week 0) to Visit 5 (Week 12), Visit 7 (Week 24), and Visit 10 (Week 52)
- Tanner pubertal stage at baseline Visit 2 (Week 0), Visit 5 (Week 12), Visit 7 (Week 24), Visit 9 (Week 40), and Visit 10 (Week 52)

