4.2.4.4 Clinical laboratory

Continuous clinical laboratory parameters will be summarized in standardized international (SI) and US conventional units.

For quantitative measurements, observed values and changes from baseline to each post-baseline visit will be determined by visit windows described in Section 4.3.1 and 4.3.3.

All hematology, clinical chemistry, growth and development hormones and urinalysis results will be listed by treatment group, patient, and visit, including scheduled and unscheduled/repeat measurements. Laboratory assessments that are outside of normal ranges will be flagged.

Baseline values, the observed values at each visit to Week 52 and including the 10-week follow-up, as well as change from baseline values will be summarized for each of the quantitative laboratory assessments by treatment group. Additionally, listings by individual patients' data will be reported as appropriate.

Clinical laboratory results (chemistry, hematology, growth and development hormones and urinalysis) will be summarized using descriptive statistics for each visit. Shift from baseline to the minimum/maximum value during treatment will be presented for the controlled assessment period and extension period, separately, based on high/low/normal findings for clinical laboratory parameters if normal ranges are available (for quantitative measurements and categorical measurements). For the categorical Urine-Blood parameters, a shift table from baseline to every planned visit will be performed. For the categorical measurements Urine Glucose, Ketones and Urine Total Protein, results will be presented under the following categories: 0, trace, +1, +2, +3.

Number and percentage of laboratory results that are potentially clinically significant (see [Appendix B3](#)) will be summarized by analyte name and criteria for each treatment group.

Estimated glomerular filtration rate will be derived based on the Bedside Schwartz formula:

$$eGFR = 41.3 * (\text{Height in meters} / \text{Serum creatinine in mg/dL})$$

A table of observed and change from baseline in eGFR values will be provided. This will be provided both overall and by baseline eGFR, hyperfiltrating versus non-hyperfiltrating, where hyperfiltration is defined as an $eGFR \geq 125 \text{ ml/min/1.73m}^2$.

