Potentially clinically significant changes are assessed with the following marked abnormality criteria for vital signs⁹:

Age: 6 - <12 years

Vital signs variables	Units	Marked abnormality criteria	
		Low	High
Heart Rate			
Value	bpm	< 60	> 95
Value - Baseline	bpm		> 20
Baseline - Value	bpm		>10
Systolic Blood Pressure			
Value	mmHg	< 100	> 120
Value - Baseline	mmHg		> 10
Baseline - Value	mmHg		>10
Diastolic Blood Pressure			
Value	mmHg	< 60	> 75
Value - Baseline	mmHg		> 10
Baseline - Value	mmHg		>10

Age: ≥12 years

Vital signs variables	Units	Marked abnormality criteria	
		Low	High
Heart Rate			
Value	bpm	< 55	> 85
Value - Baseline	bpm		> 20
Baseline - Value	bpm		>10
Systolic Blood Pressure			

Vital signs variables	Units	Marked abnormality criteria	
		Low	High
Heart Rate			
Value	mmHg	< 110	> 135
Value - Baseline	mmHg		> 10
Baseline - Value	mmHg		>10
Diastolic Blood Pressure			
Value	mmHg	< 65	> 85
Value - Baseline	mmHg		> 10
Baseline - Value	mmHg		>10

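### Protocol 6.4.3 and 6.4.3.3 conflict on when one class of laboratory or vital-sign change is an AE, and SAP Appendix B3 lacks the laboratory criteria that SAP 4.2.4.4 relies on

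*Protocol*

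**What the plan says.** **AE rules (Protocol)**

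- Section 6.4.3 covers "All clinically significant abnormalities noted upon physical examination, ECG, and clinical laboratory and vital sign measurements that occur during the study" and were absent before consent. These "should be reported as an AE, except for abnormalities present at Screening that may be considered part of the medical history". Screening findings are the only exception.
- Section 6.4.3.3, under its sub-heading on examinations and tests, opens with a reason: "The results from protocol mandated laboratory tests and vital signs will be summarized in the clinical study report". It then says that when mandated laboratory values or vital signs worsen from baseline, such changes "should therefore only be reported as AEs if they fulfil any of the SAE criteria or are the reason for discontinuation of treatment".
- The AE definition in 6.4.1 includes abnormal investigation results, with no condition about seriousness or discontinuation.

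**Use of AEs and laboratory data (SAP)**

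- Section 3.4 links the primary safety objective to "safety and tolerability endpoints including the incidence of treatment emergent AEs". The same item lists antibodies, physical examinations, laboratory measurements and vital signs.
- Section 4.2.4.1 classifies recorded AEs as treatment-emergent by timing alone.
- Section 4.2.4.4 promises a summary by analyte and criteria: "Number and percentage of laboratory results that are potentially clinically significant". It cites Appendix B3.
- Appendix B3 (section 7.3) has a title that covers laboratory variables and vital signs. Its laboratory content is one sentence pointing to the reference ranges in the laboratory manual. It continues: "Potentially clinically significant changes are assessed with the following marked abnormality criteria for vital signs". The tables that follow cover heart rate, systolic and diastolic blood pressure.

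**The concern.** Take an asymptomatic lipase rise that the investigator judges clinically significant. It is not serious and study drug continues. Under 6.4.3 it is an AE; under 6.4.3.3 it is not. Protocol 6.4.5 has investigators assess every out-of-range result for clinical significance, so the judgement that triggers 6.4.3 is made routinely.

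The SAP counts whatever sites record, so the level of TEAE incidence depends partly on which text each site applied. With about 20 centers and about 22 placebo patients, there is roughly one placebo patient per center, so site habits need not balance between arms.

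The narrower rule is justified by the results being summarized elsewhere, which makes it relevant whether those summaries are fully specified. One of them, the count of potentially clinically significant laboratory results, has no criteria from which to program it.

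**Working it through.** **1. The two rules, case by case**

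| Finding in a mandated test or examination | 6.4.3 | 6.4.3.3 |
|---|---|---|
| Meets an SAE criterion | AE | AE |
| Clinically significant and causes discontinuation of study drug | AE | AE |
| New, clinically significant physical-examination finding | AE | AE |
| Laboratory or vital-sign change with symptoms | AE | AE, recorded as the symptom |
| Clinically significant ECG finding | AE | Not restricted |
| New, clinically significant, asymptomatic, non-serious laboratory or vital-sign change, drug continued | **AE** | **Not an AE** |

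Only the last row conflicts. It cannot be read away: 6.4.3.3 goes on to make asymptomatic, clinically relevant deterioration an AE in *non-mandated* parameters, so its restriction on mandated ones is deliberate. Neither section refers to the other.

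**2. Does the SAP settle it?** No. The TEAE definition in 4.2.4.1 uses onset date relative to dosing. It has no rule for laboratory or vital-sign findings.

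**3. Scale.** The documents give no figure to reproduce here. Inputs are 77 randomized patients and 5:2 allocation (Protocol 12.7), and a 5% cut-off for the frequent-AE table (SAP 4.2.4.1).

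- Exenatide: 77 × 5/7 = 55. Placebo: 77 × 2/7 = 22.
- One patient moves incidence by 100/55 = 1.8 points (exenatide) or 100/22 = 4.5 points (placebo), if that patient has no other TEAE.
- Frequent-AE table: 0.05 × 55 = 2.75, so 3 exenatide patients; 0.05 × 22 = 1.1, so 2 placebo patients.

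The number of affected patients is not in the documents. As an assumption only, let b be the incidence of any other TEAE and q the share of the remaining patients with a finding in the conflicting row. Moving every site from the narrow to the broad rule raises an arm's incidence by (1 − b) × q:

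| | q = 5% | q = 10% | q = 20% |
|---|---|---|---|
| b = 80% | 1 point | 2 points | 4 points |
| b = 60% | 2 points | 4 points | 8 points |
| b = 40% | 3 points | 6 points | 12 points |

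Mixed practice across sites gives less than these values. They describe the level in one arm, not the difference between arms.

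**4. The Appendix B3 cross-reference.** SAP 4.2.4.4 needs a criterion per analyte. Appendix B3 supplies numerical limits for three vital signs and none for any analyte. A reference range says whether a value is normal; it does not say when a value is potentially clinically significant. The appendix shows no sign of redaction at this place.

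**5. Four markers.** The shift-table sentence in SAP 4.2.4.4 names chemistry, hematology, growth and development hormones, and urinalysis. Calcitonin, pancreatic amylase, lipase and CEA are not named. Protocol 6.4.5.5 lists them apart from the chemistry panel, and SAP Table 3.9 gives them separate visit windows. They may still fall under clinical laboratory parameters in general; the text leaves this open.

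**The case against.** Much of the safety plan does not depend on the AE rule.

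- **A reader might infer that TEAE incidence is the endpoint for the primary safety objective.** SAP 3.4 does not support this. Laboratory and vital-sign measurements stand beside it, and change in calcitonin, amylase and lipase is a safety variable in its own right.
- **A reader might infer that a patient with a large asymptomatic rise appears only in means and listings.** That is too strong. Visit summaries give minimum and maximum (SAP 4.2.4). There are shift tables where normal ranges exist, Hy's law counts and albumin-creatinine shifts (SAP 4.2.4.3 and 4.2.4.4). Protocol 11.2.1 has a sponsor medical expert review laboratory, vital-sign and ECG data for other significant AEs, with marked laboratory abnormalities as an example. For vital signs, Appendix B3 does give limits and SAP 4.2.4.5 counts patients against them.
- **A reader might infer a biased comparison with placebo.** The documents do not show one. Blinding to Week 24 makes recording that differs by arm less likely, though it gives no protection in the open-label extension.
- **A reader might infer that Appendix B3 is the stated safety net for 6.4.3.3.** Section 6.4.3.3 relies on summaries in the study report and does not mention the appendix.

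These limits stand and narrow the point. They do not remove the conflict in the one class of finding, or the missing laboratory criteria.

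**Conclusion.** This is an internal inconsistency, confined to new, clinically significant, asymptomatic, non-serious changes in mandated laboratory tests or vital signs with study drug continued. For those, the protocol gives two answers and no order of precedence, and the SAP inherits whichever a site used. The 1.8 and 4.5 points per patient assume the planned 55 and 22 patients are all dosed as allocated. The total effect is unknown, because no event rate is given, and any count of affected patients would be assumption.

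The Appendix B3 gap is separate and certain: the SAP promises a laboratory summary by criteria that it does not state. Whether calcitonin, amylase, lipase and CEA are in the shift tables is unclear; their exclusion is not established. The point merits correction but does not threaten the primary efficacy analysis.

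**What to change.** 1. Reconcile Protocol 6.4.3 with 6.4.3.3 so that one AE reporting rule for laboratory and vital-sign findings appears in both. This helps only future recording; SAP edition 2.0 already refers to a completed blinded data review.
2. Because events may already have been recorded under either rule, add to SAP 4.2.4.1 a TEAE summary with and without AEs that rest only on a laboratory or vital-sign finding. Identify these by blinded review before unblinding. The Investigations system organ class alone would miss some, since 6.4.3.3 asks for clinical terms such as anaemia over laboratory terms.
3. In SAP Appendix B3, either prespecify laboratory criteria, for example multiples of the laboratory reference limit used purely as reporting flags, or delete the cross-reference in 4.2.4.4. State in 4.2.4.4 that calcitonin, amylase, lipase and CEA are in the shift tables against reference ranges.

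Cost: a short clarification to sites, SAP wording, a blinded review and one extra table. No new data are needed. Stated TEAE counts may change slightly.
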